1.2. Adverse Event and Serious Adverse Event Collection and Reporting

Adverse occurrences or unanticipated problems reported by a subject during the course of their participation in the study will be immediately documented according to study protocol. A report will be sent to IRB if the adverse event is serious, unexpected, and related to the study. We will report to the DSMB and the National Institute on Aging (NIA) administrator all serious adverse events. For each occurrence, the PI or the designated Co-I will evaluate independently to determine severity, expectedness, and attribution of the occurrence to the study protocol or not and report to NIA, IRB, and DSMB if required per policy.

Determinations regarding adverse and serious adverse events will be made by [name] who is the designated cardiologist on the study who is unblinded. After [name] makes this final determination, the adverse event will be reported by [name] (PI) or [name] (Co-PI) to the NIA and Chair of the DSMB ([name]). All DSMB members are available in real time to review and recommend appropriate actions regarding any adverse or unanticipated events or other safety issues. Any action taken to suspend or terminate the project will be reported immediately to KUMC IRB, NIH Office of Sponsored Projects, and the study Program Officer at NIA.

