
come to the Clinical and Translational Science Unit (CTSU), a newly renovated facility with private examination rooms, pharmaceutical rooms, and storage area (for echocardiogram, i-stat instrument, etc.), and computer access to the Velos eResearch for patient data. The facility has plentiful free/close parking.

C.2. Study Design and Materials. Both HFpEF patients and stakeholders had a meaningful influence on the study design. We held focus groups, made individual phone calls, and had in-person meetings with patients with HFpEF. Our Stakeholder Advisory Panel (SAP) consists of diverse individuals including patients, caregivers, clinicians, and hospital administrators (Appendix 1) who have met three times. The patients and caregivers were particularly interested in whether ubiquinol, D-ribose, or both could enhance health status, decrease symptoms, and improve energy levels. We invited 30 HFpEF patients and their caregivers to provide input and feedback regarding the development of our research hypotheses and methods. We found their opinions extremely valuable in designing this patient-centered study.

Study Design, Including Screening, Enrollment, Visits, and Phone Follow-up (Figure 3).

Based on the power analyses (see C.5.), this randomized, double-blind, controlled trial will have a total sample size of (N) = 276. All participants will receive usual care for HFpEF. Efforts will be made to recruit 50% females, which is the actual proportion of HFpEF patients in Kansas City.

N1 = 69 subjects: Control, receive no ubiquinol and no D-ribose; placebo capsules & powder per day.
N2 = 69 subjects: Ubiquinol group, receive 600 mg of ubiquinol/day, D-ribose placebo powder per day.
N3 = 69 subjects: D-ribose group, receive 15 g of D-ribose/day, placebo capsules for ubiquinol per day.
N4 = 69 subjects: Ubiquinol + D-ribose group, receive 600 mg ubiquinol and 15 g D-ribose per day.

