Initially, potential subjects from HERON, Pioneers, and KUH outpatient HF clinics will be interviewed by phone for potential recruitment in the study. Two nurse practitioners and a cardiologist on our research team work in the outpatient HF clinics and will refer patients to us. Patients will be required to speak English, and the informed consent and patient information will be written at the 8th grade level. We will collaborate with our Human Subject Protection Program to ensure our consent form complies with the US Department of Health and Human Services (HHS) federal guidelines and obtain informed consent from eligible patients (Appendix 10). Patients that have consented will be provided a 1-week supply of placebo ubiquinol pills (instructed to take 2 pills/day) and placebo D-ribose powder (instructed to take 3 scoops/day) as a pre-randomization run-in period to evaluate compliance to the supplements. Patients will be scheduled for an appointment at the CTSU in 1 week following the run-in period. Patients that demonstrate an 80% compliance rate of ubiquinol intake (as evidenced by pill count) and an 80% compliance rate of D-ribose powder intake (as evidenced by weight of the containers) will be eligible to be randomized into a group assignment. The enrolled patients with 80% compliance will then be randomized into four groups (69 subjects in each group) to receive ubiquinol (600 mg daily), D-ribose (15 g daily), ubiquinol plus D-ribose, or placebo for a period lasting 12 weeks. Both the ubiquinol and the D-ribose supplements used in the study will have a certificate of analysis from the manufacturer (Appendix 9). The Project Director will receive the identified list of recruited subjects from the Principal Investigator (PI) and will randomly assign subjects to one of the groups using a list created by a computer-based random number generator. All supplements and the placebo will be indistinguishable in packaging and will be distributed by the Project Director independent of the PI so that the allocation of subjects to a treatment or placebo group will be concealed from both subjects and research personnel.

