All subjects will complete the demographic form at baseline. The KCCQ (Appendix 2) and Vigor scale from the Profile of Mood States (POMS) will be completed in CTSU visits at baseline and 12 weeks (Appendix 3) along with the subject's height and weight. The patient will be escorted to a private room and asked to remove clothing above the waist. A disposable gown will be provided and the patient will lay supine on the bed while an echocardiogram is completed. Approximately 0.5 ml of blood will be collected via finger stick to measure lactate, ATP, and BNP. Next, the subject will complete a 6MWT (Appendix 4, Borg scale). Approximately 2 hours will be required for each subject's visit to the CTSU. Follow-up calls will occur at 3, 6, and 9 weeks during the trial.

Potential Problem and Alternative Solutions. Serum CoQ10 and D-ribose values in some of the treatment patients might be below threshold levels at 6 weeks, possibly due to subject non-adherence. If this occurs, the Project Director, who is not blinded to the list of placebo and treatment subjects, will call and ask if there are any problems with consuming the ubiquinol and/or D-ribose. The Project Director and Research Associate will conduct a phone follow-up interview at 3, 6, and 9 weeks during the trial using a structured interview. Questions asked will relate to any side effects and compliance history in taking their capsules or powder.

Various cardiovascular risk factors will be recorded such as tobacco usage, diabetes mellitus, hypercholesterolemia, hypertension, and family history of cardiovascular disease. Smoking status will be recorded as either smoker or non-smoker. Patients who use tobacco will be given contact information for a tobacco/smoking cessation program. Diabetes mellitus will be determined by a history of the disease or use of medication for diabetes. Hypercholesterolemia will be defined as a fasting total serum cholesterol level ≥ 4.9 mmol/l or use of medication. Hypertension will be defined as either systolic or diastolic blood pressure $\geq 140/90$ mmHg or use of hypertensive medications.

C.3. Aims and Hypotheses.

AIM #1: *To determine the effects of oral ubiquinol, D-ribose, or a combination of the two administered during 12 weeks on symptoms accompanying low bioenergetics in patients with HFpEF.*

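### The final adverse-event determination rests with an unblinded study cardiologist, with no stated exception to the blinding and no stated link to the PI/Co-I evaluation

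*Combined protocol and SAP*

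**What the plan says.** **Blinding.** Section C.2 states that "this randomized, double-blind, controlled trial will have a total sample size of (N) = 276". It has the Project Director distribute supplements independently of the PI, so that "the allocation of subjects to a treatment or placebo group will be concealed from both subjects and research personnel". Section 1.1 under Participation of Human Subjects repeats the double-blind label. Later in C.2, one role is declared unblinded: "the Project Director, who is not blinded to the list of placebo and treatment subjects". No exception is made there for a cardiologist.

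**Adverse-event assessment.** DSMP 1.2 has two paragraphs on who judges an event.

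- In the first, "the PI or the designated Co-I will evaluate independently to determine severity, expectedness, and attribution of the occurrence". The same paragraph sets the IRB trigger: "A report will be sent to IRB if the adverse event is serious, unexpected, and related to the study". It also sends all serious adverse events to the DSMB and the NIA.
- In the second, determinations on adverse and serious adverse events belong to the person "who is the designated cardiologist on the study who is unblinded". Reporting by the PI or Co-PI comes after that step; once the cardiologist "makes this final determination, the adverse event will be reported by" one of them.

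**The concern.** Severity, expectedness and relatedness are judgements, and blinding exists to keep knowledge of the arm out of judgements like these. The plan's own account of likely side effects shows how much judgement is involved. Section 1.3 under Participation of Human Subjects and DSMP 1.1 list diarrhea, gastrointestinal discomfort and nausea. Section 1.3 adds that mild gastrointestinal symptoms were seen on both ubiquinol and placebo in earlier work. Whether such an event is caused by the supplement is hard to settle on clinical grounds, so an assessor who knows the allocation may lean on it.

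The direction cannot be predicted. Events on active treatment could be attributed too readily. They could also be dismissed, since the plan expects no appreciable risk.

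Two uses of the judgement are at stake: which events reach the IRB, and how adverse effects are described by arm when the DSMB makes the recommendations listed in DSMP 3.6.

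**Working it through.** The plan gives no adverse-event rates and no power basis for safety, so there is no figure to reproduce and no formula to apply. The check is a comparison of the texts.

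1. **Is the final assessor unblinded?** Yes. DSMP 1.2 says so directly and labels the determination final. No inference is needed.

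2. **Does the blinding section allow for this?** No. C.2 conceals allocation from research personnel. A cardiologist described as being on the study falls within that term. The Project Director is the only other role stated to be unblinded, and no reason is given for unblinding the cardiologist.

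3. **How do the two paragraphs of DSMP 1.2 relate?** Three readings are possible:
   - Two steps: the PI or Co-I evaluates first, and the cardiologist then decides.
   - Two competing assignments of the same task.
   - One role: the cardiologist is the designated Co-I.

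   Names are removed from the available copy, so the choice cannot be settled. On the first reading the unblinded view prevails. On the second the plan does not say whose judgement is recorded. On the third a blinded assessment is not assured. No reading makes a blinded judgement the one of record.

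4. **Is a blinded assessor available?** Yes. C.2 keeps distribution independent of the PI in order to conceal allocation, and DSMP 1.2 already has the PI or Co-I evaluate each event. The blinding status of the Co-I is not stated.

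5. **What depends on the judgement?**

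| Item | Depends on judged severity, expectedness or relatedness? |
|---|---|
| IRB report | Yes: expectedness and relatedness are two of its three conditions |
| By-arm description of adverse effects for the DSMB | Yes, where events are summarised by severity or relatedness |
| Serious events to the DSMB and NIA | Not on relatedness: all are reported |
| Raw event counts | Largely not: events are documented when a subject reports them |
| Planned hypothesis tests in C.5 | No: none concerns safety |

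The third and fourth rows are less exposed, not immune. DSMP 1.2 does not say whether the cardiologist's determination includes whether an event is serious. The unblinded Project Director also shares the calls at weeks 3, 6 and 9 that ask about side effects.

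**The case against.** The best defence has four parts.

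**An unblinded safety physician is a legitimate role.** This stands. The plan also declares the Project Director unblinded, so the concealment statement was never literally universal. What remains is that this person's judgement is final, with no stated reason, no exception in C.2 and no requirement that a blinded assessment be recorded first.

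**The two paragraphs may describe a sequence.** This also stands. A reader might infer that DSMP 1.2 contradicts itself, but the text supports only the statement that the relation between the two assessments is not given.

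**Other safeguards exist.** They do. All serious events go to the DSMB and NIA whatever their attribution. The DSMB is to include external scientists, among them a cardiologist and a biostatistician (DSMP 3.3), and its members are available to review events in real time. This limits the consequence for serious events. It does not help with attribution of non-serious events, or with the IRB trigger.

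**No planned analysis is affected.** This is correct. Section C.5 specifies no between-arm safety comparison, and none of the six hypotheses concerns safety. A reader might take related-event rates by arm to be a principal safety result of the trial; the documents do not define such a result.

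**Conclusion.** The point holds in a limited form. The plan gives the final adverse-event determination to someone who knows the allocation, does not reconcile this with the concealment statement in C.2, and does not say how it relates to the PI/Co-I evaluation. Judged severity, expectedness and relatedness can be influenced by knowledge of the arm, and through them IRB reporting and by-arm descriptions to the DSMB.

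The size of the bias cannot be derived. Any figure would need an assumed event rate and assumed attribution rates by arm, and would only restate those assumptions.

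A reader might also infer that the unblinded cardiologist reads the echocardiograms, so that E/e' is assessed unblinded. The documents do not support this. The readers under Hypothesis #3 and the cardiologist in DSMP 1.2 are both identified by names removed from the available copy, so whether they overlap cannot be determined. The efficacy analysis and sample size are not put in question here.

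The conclusion assumes that the PI is blinded, as C.2 implies, and that a cardiologist on the study counts as research personnel. The change should be made because it corrects a stated rule at very little cost.

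**What to change.** In DSMP 1.2:

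- Have the blinded PI, or a Co-I confirmed as blinded, record severity, expectedness and attribution for each event before any input from someone who knows the allocation.
- Make that record the determination used in the safety dataset and in by-arm summaries.
- Limit the unblinded cardiologist to cases that need the allocation, and record any later change separately, leaving the blinded entry intact.

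In C.2, name every unblinded role, with the reason for each, so that the concealment statement and DSMP 1.2 agree.

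The cost is wording in two sections and a little more documentation per event. The PI or Co-I already evaluates each event, so no new assessor is needed provided the PI is blinded. If the designated Co-I proves to be the unblinded cardiologist, the PI or another blinded Co-I has to take the first assessment.

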1.3. Protection Against Study Risks

Informed Consent Process: The consent process will inform a volunteer about the study, indicating the participation is voluntary and he/she has the right to stop at any time. Risks will be enumerated in the informed consent form and described orally during the consent process.

Protection Against Risks: Although no appreciable risk of physical or mental harm is expected to result from the proposed protocol, procedures for dealing with adverse effects are established. Participants will be instructed to take the supplements (ubiquinol, D-ribose, a combination, or placebo) with a meal to prevent or minimize gastrointestinal symptoms. The procedures listed below will be followed to avert negative reactions to procedures or questions posed during the CTSU visits or the follow-up telephone calls: 1) all subjects will be informed that they are free to skip questions, 2) end data collection, 3) not participate in any component of clinical evaluation and laboratory testing, or 4) withdraw from the study without changes in their standard or usual medical or nursing care. Subjects will be instructed to report immediately to the PI, Project Director, Research Associate or the cardiologists (consultants) any negative side effects when consuming the supplements. Appointments will be cancelled and rescheduled if subjects express an inability to travel for scheduled CTSU visits. Furthermore, personnel are trained to discontinue any data collection in which the participant becomes emotionally upset or notes discomfort. The Research Associate or the PI will refer that person to our cardiologists or call 911, if immediate medical assistance is required. Subjects who express worry or distress from perceived loss of privacy, have concerns about inconvenience or rights as a research subject (explained in the consent form), will be assured that they do not have to participate, that their medical

care will not be affected, or if already enrolled in the study that they may withdraw at any time without prejudice. In addition, any such concerns will be documented and reported to IRB.

2.0 Interim Analysis

There are no advance plans for interim and/or futility analysis at this time.

3.0 Data and Safety Monitoring

The Principal Investigator (PI) will be responsible for ensuring participants' safety on a daily basis. The DSMB will act in an advisory capacity to the NIA Director to monitor participant safety, evaluate the progress of the study, to review procedures for maintaining the confidentiality of data, the quality of data collection, management, and analyses.

3.1. Frequency of Data and Safety Monitoring

The DSMB will meet annually to evaluate the study progress, either in-person or by teleconference call to review study progress, data quality, and participants safety. The PI ([name]) will be informed of serious adverse events as soon as they occur and will notify the NIA and the DSMB within 2 business days of notification.

3.2. Content of Data and Safety Monitoring Report

The content of the data and safety monitoring report will include: study status, participant descriptive information, safety information, and study quality. Prior to subject recruitment, the members of the DSMB will read the written study protocols, informed consent procedures, Data Safety Monitoring (DSM) policies, and plan.¹⁰⁰ Members of the DSMB will initially discuss the plan for clarification of their responsibilities, the board structure, and organization and rules of operation, as noted in the policies. All trial progress and DSMB advice on continuation, modification, or termination are reported to the Principal Investigator ([name]), IRB, and the NIA Program Officer.

3.3. DSMB Membership and Affiliation

Each of the individuals will formally accept the position as part of the DSMB and the DSMB membership will be reviewed and approved by the NIA. Should there be any questions regarding the independence of the DSMB, it will be addressed and corrected if necessary at that time. This DSMB will include external scientists (cardiologist, supplemental specialist, and a biostatistician) selected and chosen by NIA.

3.4. Conflict of Interest for DSMB's

DSMB members will have no direct involvement with the study investigators or intervention. Each DSMB member will sign a Conflict of Interest Statement which includes current affiliations, if any, with pharmaceutical and biotechnology companies (e.g., stockholder, consultant), and any other relationship that could be perceived as a conflict of interest related to the study and/or associated with commercial interests pertinent to study objectives.

3.5. Protection of Confidentiality

Data will be presented in a blinded manner during the open sessions of the DSMB. At DSMB meetings, data and discussion are confidential. Participant identities will not be known to the DSMB members.

3.6. DSMB Responsibilities

If approved by NIA, the DSMB Charter responsibilities will include:

- Review the research protocol, informed consent documents and plans for data safety and monitoring;
- Recommend subject recruitment be initiated after receipt of a satisfactory protocol;
- Evaluate the progress of the trial, including periodic assessments of data quality and timeliness, recruitment, accrual and retention, participant risk versus benefit, performance of the trial sites, and other factors that can affect study outcome;
- Consider factors external to the study when relevant information becomes available, such as scientific or therapeutic developments that may have an impact on the safety of the participants or the ethics of the trial;

- Review study performance, make recommendations and assist in the resolution of problems reported by the Principal Investigator ([name]);
- Protect the safety of the study participants;
- Report to NIA on the safety and progress of the trial;
- Make recommendations to the NIA and the Principal Investigator concerning continuation, termination or other modifications of the trial based on the observed beneficial or adverse effects of the treatment under study;
- If appropriate, review interim analyses in accordance with stopping rules, which are clearly defined in advance of data analysis and have the approval of the DSMB;
- Ensure the confidentiality of the study data and the results of monitoring; and,
- Assist the NIA by commenting on any problems with study conduct, enrollment, sample size, and/or data collection.
- The DSMB will evaluate the final study manuscripts and final reports to assure results are fairly presented and conclusions are appropriate.¹⁰¹

Inclusion of Women and Minorities.

Subjects may participate regardless of gender, socioeconomic level, or ethnic background. All subjects will be 50 years or over, as HFpEF is more prevalent in older adults. National statistics show the prevalence of heart failure to be divided roughly equally between males and females.¹⁰² Efforts will be made to recruit 50% females, which is the actual proportion of HFpEF patients in Kansas City.

The regional HF statistics indicate are: 10% Black/African Americans (AA), 13% Hispanic/Latino, 76% White, and 1% Asian, Native American/Alaskan Native, Native Hawaiian/Pacific Islander. The racial and ethnic population distribution planned coincides with these national and regional figures. The Kansas City Metropolitan Statistical Area confirms these percentages in the general population.⁹⁹ In this study, we will oversample minorities (reviewer's suggestion), which will enable us to examine the relationship between HFpEF and racial/ethnic differences. Most of the data regarding treatments for HFpEF are derived from white populations,²⁷ and therefore it is important to include other racial/ethnic groups and examine whether the effects of ubiquinol and/or D-ribose follow similar patterns to those among whites. For this study, a total of 276 subjects will be randomized to one of the four groups. As suggested by the reviewers, we will oversample minority populations to increase the generalizability of data for minority groups (30% Black/AA, 30% Hispanic/Latino, 30% White, and 10% Other). Each group will be Black/AA = 21, Hispanic/Latino = 21, White = 21, American Indian/Alaska Native, Asian, Native Hawaiian/Pacific Islander = 6 (Total = 69). The University of Kansas Medical Center (KUMC) Healthcare Enterprise Repository for Ontological Narration (HERON) database, Pioneers Recruitment Registry (Pioneers), and chronic HF clinic at the University of Kansas Hospital (KUH) will be used to recruit subjects. These registries provide clinical/translational investigators with the numbers of patients at KUH who meet the inclusion criteria for clinical trials and contact information for patients who sign up with KUMC's Frontiers participant registry. Based on the HERON, there will be approximately 7,100 subjects with HFpEF available to be screened for enrollment in this study. The Swope Health Services in Kansas City, Missouri has a large Black/AA and Hispanic/Latino population. The Pioneers Registry has a relationship with Swope Health Services and can assist us with electronic informed consent forms, email verification, and subject recruitment at this site.

Inclusion of Children.

All subjects will be 50 years or over, as HFpEF is more prevalent in older adults. Children (the age to 18 years and younger) will not be included in this study because diastolic heart failure is very rare in the pediatric population.

